11. STATISTICAL ANALYSIS

Data of completing subjects will be included for all statistical analyses. Descriptive statistical summary will be performed including N, mean, median, standard deviations, minimum, and maximum of values at all applicable time points and for both treatments.

Comparison between the study treatments will be made in terms of changes from baseline. The null hypothesis, that the mean change from baseline is equal between the 2 study treatments at post-baseline time point, will be tested using methods described in the Statistical Analysis Plan table.

Protocol Version: 04

This document contains confidential, proprietary information.

Statistical Analysis Plan

Evaluation	Change from Baseline	Comparisons between study treatments	Notes/Interpretation
Volume change by 3D imaging analysis	Paired t-test; If normality fails, a Wilcoxon signed-rank test will be used.	Wilcoxon rank-sum test or sample t-test	A higher value reflects an improvement in skin volume.

Statistical analysis for gene expression will be determined using the relative quantification method.

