5. STUDY OBJECTIVES AND CLINICAL HYPOTHESIS

5.1 Study Objectives

The primary objective of this study is to compare gene expression stimulated by a semi-permanent filler and a biostimulator via punch biopsy.

The secondary objective of this study is to assess and compare volume change in the NLF via clinical photography.

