6. SELECTION AND DISPOSITION OF STUDY POPULATION

6.1 Number of Subjects

An appropriate number of subjects meeting inclusion/exclusion criteria listed below will be enrolled on the study to achieve maximum 20 subjects who complete the study as planned.

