7.6 Treatment Dosage and Mode of Administration

The injection technique (skin disinfection material, type of syringe, type and gauge of the intradermal needle, penetration angle, depth) will be the technique customarily used by the Investigator. The type of gauge of the injection needle will be recorded in the CRFs.

PLLA: two treatment sessions at 4-week interval with the first treatment at Visit 1 and the second treatment at Visit 3. Each treatment session will be consisted of multiple deep dermal injections, up to 9 mL/session (or up to 4.5 mL/NLF/session), into the left and right NLFs of each subject according to the IFU. The treatment amount for each PLLA subject will be determined at the Investigator discretion to achieve an optimal correction. Within each PLLA subject, the amount of each treatment needs to be equal at the left and right NLFs because of the identical WAS scores. The treatment volume injected during each treatment session for each subject will be recorded in the CRFs.

CaHA: up to two treatment sessions at 4-week interval with the required first treatment at Visit 1 and an optional second treatment at Visit 3 to achieve an optimal cosmetic correction. Each treatment session will be consisted of multiple subdermal injections, up to 1.5 mL/session (or up to 0.75 mL/NLF/session), into the left and right NLFs of each subject according to the IFU. The second treatment is optional and will be determined based on the Investigator assessment. If the subject needs a second treatment, an appropriate amount will be determined at the Investigator discretion to achieve an optimal outcome. The amount of each treatment needs to be equal at the left and right NLFs because of the identical WAS scores. The treatment volume injected during each treatment session for each subject will be recorded in the CRFs.

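### Gene expression, the primary objective, is to be compared on changes from baseline with no baseline covariate named; ANCOVA on each gene's baseline is more precise at low to moderate correlation if the two SDs are similar

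*Combined protocol and SAP*

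**What the plan says.** Section 5.1 sets the aim: "The primary objective of this study is to compare gene expression stimulated by a semi-permanent filler and a biostimulator via punch biopsy". Section 11 then gives a general rule, not limited to one endpoint: "Comparison between the study treatments will be made in terms of changes from baseline". The hypothesis to be tested is "The null hypothesis, that the mean change from baseline is equal between the 2 study treatments at post-baseline time point", using the methods in the SAP table.

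That table has a single row, for volume by 3D imaging, with a rank-sum or t-test between products and no covariate. Gene expression is dealt with in one sentence after the table: "Statistical analysis for gene expression will be determined using the relative quantification method". This names no between-product test, model or covariate. Baseline adjustment is not mentioned anywhere in the document.

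The sample is small. Section 6.1 enrols "to achieve maximum 20 subjects who complete the study as planned", the Synopsis puts 10 in each group, and Section 11 adds "Data of completing subjects will be included for all statistical analyses". Under Section 10.3 each subject gives one baseline biopsy from one fold and one Day 84 biopsy from the other.

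**The concern.** Read as written, the primary comparison is of mean change, which is a model with the baseline slope fixed at 1 for every gene. Nothing in the document supports a slope of 1 across a panel covering at least eleven biomarker classes. Tissue from opposite folds, 12 weeks apart, may be only modestly correlated, and the correlation may differ between genes. If it is modest and the two SDs are similar, subtracting baseline adds more noise than it removes.

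With at most 20 completers, precision is scarce. An unadjusted change score would give up precision that the planned baseline biopsies could supply at no extra procedure. Bias is not the issue: product and biopsy side are randomized (Section 7.5), and both folds must have the same WAS score (Section 6.3).

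**Working it through.** **Nothing to reproduce.** The figure of 20 completers comes with no alpha, power, effect size, SD or correlation.

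**Inputs from the document.** N = 20 completers, 10 per arm (Synopsis, Section 6.1); one baseline and one Day 84 value per gene per subject (Section 10.3).

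**Assumed inputs, shown as ranges.** The baseline to Day 84 correlation r, and k = Day 84 SD / baseline SD. The formulas also assume a normal covariate, a common slope and equal arms.

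**Formulas (baseline SD set to 1).**
- Change-score variance: 1 + k² − 2rk
- ANCOVA variance with known slope: k²(1 − r²)
- Difference: (1 − rk)², never negative
- Factor for estimating the slope: 1 + 1/(N − 4), which is 1.0625, 1.0714 and 1.0833 at N = 20, 18 and 16
- Ratio of ANCOVA to change score: k²(1 − r²) × factor / (1 + k² − 2rk)

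Example, k = 1 and r = 0.4: 0.84 / 1.20 = 0.70, and 0.70 × 1.0625 = 0.74.

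**Variance ratio at N = 20** (below 1 favours ANCOVA):

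| k | r = 0.2 | 0.4 | 0.6 | 0.8 | 0.9 | ANCOVA less precise for |
|---|---|---|---|---|---|---|
| 0.8 | 0.49 | 0.57 | 0.64 | 0.68 | 0.65 | no r |
| 1.0 | 0.64 | 0.74 | 0.85 | 0.96 | 1.01 | r above 0.88 |
| 1.25 | 0.77 | 0.89 | 1.00 | 1.06 | 1.01 | r 0.60–0.91 |
| 1.5 | 0.87 | 0.98 | 1.06 | 1.01 | 0.83 | r 0.44–0.81 |
| 2.0 | 0.97 | 1.05 | 1.05 | 0.85 | 0.58 | r 0.26–0.68 |

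With equal SDs the break-even follows directly: (1 + r)/2 × 1.0625 = 1 gives r = 2/1.0625 − 1 = 0.88. At 16 completers the gain ends earlier, at r = 0.85, 0.56, 0.40 and 0.22 for k = 1, 1.25, 1.5 and 2.

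**What the equal-SD row means.** The 95% CI width ratio, including the lost degree of freedom (17 against 18), is 0.80, 0.87, 0.93, 0.98 and 1.01. To match ANCOVA at 10 per arm, change scores would need 10/ratio = 15.7, 13.4, 11.8, 10.5 and 9.9 per arm. For an assumed true difference of 1 SD and two-sided alpha of 0.05, simulated power is 44% (change) against 58% (ANCOVA) at r = 0.3, and 56% against 66% at r = 0.5.

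**Worst case.** The ratio cannot exceed the factor, which it reaches when rk = 1, that is, when the true slope is 1. The expected variance loss is therefore at most 6.25%, 7.1% and 8.3% at 20, 18 and 16 completers. Multiplying the factor by (t on N − 3 df / t on N − 2 df)² gives 1.0715, 1.0831 and 1.0991 for squared CI width, so the CI is at most 3.5%, 4.1% or 4.8% wider.

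**Simulation check** (60,000 runs per cell, N = 20). Equal SDs: 0.641, 0.750, 0.849, 0.953, 1.011. For k = 1.5: 0.868, 0.977, 1.057, 1.014, 0.827. For k = 2: 0.972, 1.050, 1.047, 0.852, 0.575. ANCOVA type I error was 4.8–5.2% over all simulated cells at N = 20, 18 and 16.

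All figures are per gene. Multiplicity across the panel is a separate question.

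**The case against.** The strongest reply is that no sentence commits the sponsor to an unadjusted test of gene expression. The change-from-baseline sentence does not forbid a covariate, and ANCOVA of change with baseline as covariate gives the same product effect as ANCOVA of the Day 84 value. The larger gap is that the primary comparison has no named test at all. This stands, and it is why the unadjusted reading is described as an inference. It does not remove the point: whoever fills the gap must choose a model, and the general sentence steers towards the change score.

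The second reply is that the benefit depends on unseen inputs. In the grid above, 7 of 25 cells favour the change score and 11 have a ratio of 0.95 or more. A larger Day 84 SD is plausible, because injected amounts vary: "The treatment amount for each PLLA subject will be determined at the Investigator discretion to achieve an optimal correction", and for CaHA, "The second treatment is optional and will be determined based on the Investigator assessment". The same face and matched WAS scores could also support a high r. This is fair, and it limits the claim to similar SDs and low to moderate r. The trade is still lopsided, with a capped loss of 6.25% of variance against a gain of 36% at r = 0.2 with equal SDs. If the Day 84 SD differs by arm (1 and 2 times baseline, r = 0.6), the simulated ratio is 1.05: no gain, but within the cap.

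Three smaller points also stand. ANCOVA as proposed has no fallback for non-normal data, whereas the volume row has rank-based options. The document does not say whether the outside laboratory returns separate baseline and Day 84 values. And the statement about bias relies on randomization, which a completers-only analysis can weaken if completion differs by product; that affects both methods, and neither cures it.

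**Conclusion.** The concern holds as a conditional loss of precision in the primary comparison. With similar SDs and r of about 0.2 to 0.6, an unadjusted change score forgoes roughly 15% to 36% of the variance at 10 per arm. The advantage shrinks to about 4% at r = 0.8 and is gone above r = 0.88. With a Day 84 SD 1.5 to 2 times baseline, ANCOVA gains little or loses slightly over the middle range of r, within the stated ceiling.

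The result rests on assumed values of r and k, a normal covariate, a common slope and equal arms, and on reading Section 11 as applying to gene expression without a covariate. Confidence is medium. The plan should be changed, but a change-score analysis would not be invalid.

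**What to change.** Add a gene-expression row to the SAP table in Section 11. For each gene, specify ANCOVA of the Day 84 log-scale relative expression on product, with that gene's baseline value as covariate, and report the adjusted product difference with its 95% CI. The scale has to be named; delta-Ct is one possibility, but it is an assumption here because the document names none. Keep the unadjusted change comparison as a sensitivity analysis, where the rank-sum option from the volume row could serve for clearly non-normal data. Fix the choice before any expression data are seen, so that the model is not picked gene by gene.

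The cost is SAP wording, plus confirmation that the laboratory will supply baseline and Day 84 values separately for each subject. No visit, biopsy or assay is added. The statistical price is one degree of freedom and the bounded variance loss shown in the working.

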1. SYNOPSIS

Primary Study Objective	To compare gene expression stimulated by a semi-permanent filler and a biostimulator via punch biopsy
Secondary Study Objective	To assess and compare volume change in the nasolabial fold via clinical photography
Methodology	Randomized, single-center, comparative study
Number of Subjects	20 subjects to complete (10 subjects per treatment product group)
Study duration	13 weeks total
Study treatment products	Sculptra® - poly L-lactic acid (PLLA) biostimulator Radiesse® (+) – calcium hydroxylapatite (CaHA) semi-permanent filler
Conditions of use	Per on-label instruction
Study visits	Visit 1 (Day 0/baseline), visit 2 (day 5), visit 3 (day 28/week 4), visit 4 (day 84/week 12), and visit 5 (day 89).
Specific Inclusion Criteria:	
 ○ Demographics and study skin conditions 
 - Any race and ethnicity (to be recorded) - Fitzpatrick skin type (to be recorded) - Women or men - Age: 22-50 years old - Subject with a minimum of shallow nasolabial fold (NLF) contour deficiencies as assessed via the wrinkle assessment scale (WAS) - Subject with identical WAS scores on both NLFs - Subject who in the opinion of the treating Investigator would only need 2 treatments for optimal clinical outcomes - Subject with healthy immune systems ○ Administrative 
 - Ability of giving consent for participation in the study - Agreement to have skin biopsies on NLFs

	
 - Agreement to adhere to the procedures and requirements of the study and to report to the institute on the day(s) and at the time(s) scheduled for the assessments

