7.5 Method of Treatment Assignment

Before the start of the study, a randomization list will be prepared by the Sponsor utilizing a computer-generated software. This will randomly assign the study product to each enrolled subject and the NLF side for punch biopsy.

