10.3 Punch Biopsy Collection and Analysis

At baseline/day 0 and day 84, subjects will participate in a 3-mm punch biopsy procedure (post-photography and pre-treatment). Each subject will have 1 biopsy at one side of the NLF (based on the pre-determined randomization) at baseline and 1 biopsy at the other side of the NLF at day 84; total of 2 biopsies per subject at both timepoints.

Biopsies will be obtained using standard sterile technique after an intradermal local anesthesia and treated with topical antibiotic and sterile dressing in routine fashion (see Appendix I: Biopsy Procedure and Post-Care).

The biopsy specimens will be immediately transferred into RNAlater solution and stored at room temperature for 4 hours and then moved to 4°C. Collected biopsy samples will be sent to the following address for gene expression analysis on icepack (4°C).

The biopsy sample will contain the subject number/identification (baseline and day 84), product information, and any other relevant information needed to identify the samples post-analysis.

Attn: [name]
Genemarkers, LLC
[name]
[name]
[contact]

Gene expression analysis will be performed via qPCR processing using a panel of biomarkers related to scar tissue formation, collagen, elastin, extracellular matrix integrity, epidermal barrier, anti-aging, antioxidant, cell renewal/regeneration, inflammation, growth factor, and hydration among others.

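### Gene-expression change contrasts opposite folds, yet the randomised biopsy side is neither stated to be balanced within product nor used in the analysis; the cost is possible loss of power, not bias on average

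*Combined protocol and SAP*

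**What the plan says.** Section 5.1 makes the gene-expression comparison the primary objective: "The primary objective of this study is to compare gene expression stimulated by a semi-permanent filler and a biostimulator via punch biopsy". The synopsis plans 20 completers, 10 per product.

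Section 10.3 takes one specimen per time point. The first comes from the randomised fold at baseline, followed by "1 biopsy at the other side of the NLF at day 84". The synopsis and Section 9.1.4 describe the same layout. Section 7.5 says of the sponsor's computer-generated list: "This will randomly assign the study product to each enrolled subject and the NLF side for punch biopsy". It does not mention blocking, stratification or balance of side within product.

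Section 11 gives the general rule: "Comparison between the study treatments will be made in terms of changes from baseline". The table that follows has one row, for 3D volume, with "Wilcoxon rank-sum test or sample t-test" as the between-product test. For gene expression the section adds only: "Statistical analysis for gene expression will be determined using the relative quantification method". Biopsy side does not appear in Section 11.

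**The concern.** With one biopsy per fold, no subject has a before-and-after measurement on the same fold. If expression of a gene differs on average between left and right, that difference enters the change score with one sign for subjects biopsied left first and the opposite sign for those biopsied right first. The design controls side order by randomising it. The analysis, as far as it is written, then ignores it.

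With 10 subjects per product, two things can follow. The left-right difference is counted as residual noise and lowers power. Or, if one product happens to have more left-first subjects, part of the difference shows up in that trial's product contrast. Volume does not have this problem, because Section 10.2 measures the change on each fold.

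**Working it through.** **Inputs from the documents.** 10 completers per product (synopsis); opposite-fold biopsies (Section 10.3); randomised side with no stated balancing (Section 7.5). The plan gives no alpha, power, effect size or SD, so it has no figure to reproduce.

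**Assumptions.** Two-sided alpha 0.05. The unit is the SD of the change score among subjects with the same side order. Delta is the average left-minus-right difference in that unit. The documents do not give it, so the range 0 to 1 is shown. The comparator is an unadjusted two-sample t-test.

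**1. Benchmark effect.** By the normal approximation, 10 per arm has 80% power at sqrt(2/10) × (1.960 + 0.842) = 1.25 SD. With the t distribution on 18 df the value is 1.32 SD, which is used below.

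**2. How delta enters.** A left-first subject's change is right at Day 84 minus left at Day 0, so it contains −delta. A right-first subject's change contains +delta. With k left-first subjects of 10, the arm mean moves by delta × (10 − 2k)/10. With k1 and k2 left-first subjects in the two arms, the product contrast moves by 0.2 × |k1 − k2| × delta in absolute size.

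**3. Chance imbalance.** If side is randomised independently for each subject (two binomials, n = 10, p = 0.5):

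- P(|k1 − k2| ≥ 2) = 50%, a shift of at least 0.4 delta.
- P(|k1 − k2| ≥ 4) = 11.5%, a shift of at least 0.8 delta.

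If side is 10/10 overall but not balanced by product, these probabilities are 66% and 18%. The shift averages zero over the randomisation.

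**4. Added variance.** With simple randomisation of side, the SD of change is multiplied by sqrt(1 + delta²): 1.03, 1.12 and 1.41 at delta 0.25, 0.5 and 1.0.

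**5. Power and type I error.** Results are from 40,000 simulated trials per setting; the simulation error of a power near 80% is sqrt(0.8 × 0.2/40,000) = 0.2 points. The adjusted analysis is a linear model with product and side order, on 17 df.

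| Side allocation | Delta (SD) | Power, no side term | Power, side term | Type I error, no side term |
|---|---|---|---|---|
| Simple | 0 | 79.9% | 77.4% | 5.1% |
| Simple | 0.25 | 77.8% | 77.7% | 4.9% |
| Simple | 0.5 | 70.6% | 77.2% | 4.9% |
| Simple | 1.0 | 50.3% | 77.7% | 5.2% |
| 5/5 in each arm | 0 | 79.6% | 79.3% | 5.0% |
| 5/5 in each arm | 0.25 | 78.2% | 79.8% | 4.3% |
| 5/5 in each arm | 0.5 | 72.3% | 80.0% | 2.8% |
| 5/5 in each arm | 1.0 | 48.2% | 79.8% | 0.5% |

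Type I error with the side term was 4.8-5.0% in every setting.

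**6. Why balance alone is not enough.** With 5/5 in each arm, delta cancels from the product contrast but stays in the residual. It adds 20 × delta²/18 = 1.11 × delta² to the estimated variance. The standard error is then too large, which explains the type I error of 2.8% and 0.5%.

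**The case against.** The strongest reply is that the figures for an analysis without a side term describe an assumed t-test, not the sponsor's analysis. This stands. The one-row table covers volume, and Section 11 names no between-product test for gene expression. That missing test is a larger, related gap. It does not remove this point, because any analysis of change from baseline on these specimens is a cross-fold contrast, and the test still to be written will either use side or not.

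The second reply is that delta may be close to zero. Sections 6.3 and 6.4 require identical wrinkle scores on both folds and exclude significant asymmetry. Section 7.6 requires equal left and right volumes for both products. This largely stands as well. The rules act on visible wrinkles and dosing, not on gene expression, so they do not show that delta is zero. They do make 1 SD a speculative end of the range.

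Third, a side term can cost more than it gains. Under simple randomisation it loses about 2.5 points at delta 0 (79.9% against 77.4%) and breaks even near 0.25 SD. Also, silence in Section 7.5 does not prove that the list is unbalanced.

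A reader might infer that the opposite-fold design biases the product comparison or raises the false-positive rate. The documents do not support that. Side is randomised, so the average shift is zero. Without a side term, type I error is near 5% under simple randomisation and below 5% when delta is non-zero and sides are balanced.

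**Conclusion.** The point holds as one of efficiency and of chance imbalance within a single small trial. At 10 per arm, two-sided alpha 0.05 and a true effect of 1.32 SD, leaving side out costs about 2 points of power or less at delta 0.25 SD, 7 to 9 points at 0.5 SD and about 30 points at 1.0 SD. Balancing side within product and modelling it keeps power at 79-80% across that range. The size depends wholly on delta, which the documents do not supply and which may be small. A side term removes only the average left-right difference; subject-specific asymmetry and punch-to-punch variation remain. Priority is minor to moderate.

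**What to change.** Make both changes together.

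1. **Section 7.5:** generate the list in permuted blocks over the four cells (product by first-biopsy side). With 20 subjects this gives 20/4 = 5 per cell. If replacements are enrolled, balance among completers will be approximate, and the model handles that.
2. **Section 11:** state that products are compared on gene-expression change from baseline with a linear model containing product and first-biopsy side. This also supplies the between-product analysis that the section lacks for the primary outcome. Section 10.3 does not list side among the specimen details, so the side actually biopsied should be recorded with each specimen.

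The cost is one list setting, a sentence in the analysis section and one degree of freedom (17 instead of 18). At delta 0 that is under 1 point of power with balanced cells (79.6% against 79.3%). If the list cannot be balanced, the cost at delta 0 is about 2 to 3 points, and the side term gains power only above a delta of about 0.25 SD. No extra subjects, visits or biopsies are needed.

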10.2 Clinical Photography (Cherry Imaging)

Three (3) dimensional images of the subject's face will be taken at baseline/day 0 (pre-biopsy and pre-treatment), day 28 (pre-treatment), and day 84 (pre-biopsy).

Protocol Version: 04

This document contains confidential, proprietary information.

Protocol GLI.04.US.SL.020

CONFIDENTIAL

Clinic staff needs to ensure subjects to have a clean face with no makeup, no facial hair, and to remove any jewelry from the area to be photographed. Subjects will be provided with a headband to keep hair away from the face. Subjects will be instructed to adopt neutral, nonsmiling expression with their eyes gently closed, and in a relaxed positioned for each scan.

A total of three 3D images will be taken of each subject's face using the Cherry Imaging device (Cherry Imaging, Israel). The Cherry Imaging relies on multi-directional illumination and computer-aided reconstruction of the skin surface in 3D.

Change in volume on each NLF will be analyzed by the Cherry Imaging software.

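### Does Section 11 need to name the unit of analysis for volume change, and to treat the fold biopsied at Day 0 separately?

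*Combined protocol and SAP*

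**What the plan says.** Section 5.1 sets the endpoint in its place: "The secondary objective of this study is to assess and compare volume change in the NLF via clinical photography". Section 10.2 describes the measurement per fold: "Change in volume on each NLF will be analyzed by the Cherry Imaging software". Images are taken at baseline before biopsy and injection, at Day 28 before any injection, and at Day 84 before the second biopsy.

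Product is assigned to the subject. The same randomisation list picks which fold is biopsied at Day 0 (Section 7.5), and the Synopsis plans 10 completers per product. Both folds must have the same wrinkle score at entry (Section 6.3) and receive equal amounts of product (Section 7.6).

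Section 11 states the hypothesis between products: "The null hypothesis, that the mean change from baseline is equal between the 2 study treatments at post-baseline time point". It defines who is analysed: "Data of completing subjects will be included for all statistical analyses". The table gives "Paired t-test; If normality fails, a Wilcoxon signed-rank test will be used" for change from baseline and "Wilcoxon rank-sum test or sample t-test" for the product comparison. It contains no rule for combining two folds and none for the fold biopsied at Day 0.

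**The concern.** Two folds in each of 20 completers give 40 volume changes, and the named tests require independent observations. A subject's folds should be positively correlated: they start at the same wrinkle grade and receive equal amounts, while the amount varies between subjects. An analyst who entered 20 folds per arm would break no sentence of Section 11. The standard errors would be too small in both the within-arm and the between-product tests.

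The second worry is the biopsy. At Days 28 and 84 one fold per subject has had a 3-mm punch closed with 1 to 3 sutures (Section 10.3, Appendix I) and the other has not. Visit 5 provides for a scar assessment, so the protocol itself allows that the site may be altered. A within-arm change that uses both folds could mix a biopsy effect with the product effect, although every subject has a fold that is unbiopsied at all three images.

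**Working it through.** The plan states no power, significance level or sample-size derivation, so there is no figure to reproduce.

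**Inputs.** From the documents: 10 completers per product, two folds each, product assigned by subject. Assumed: two-sided 5% level; correlation ρ between a subject's two fold changes of 0.2, 0.5, 0.8 or 0.9; normal data with equal variances. SD means the SD of one fold's change from baseline.

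**1. If folds were treated as independent.** The true variance of a 20-fold arm mean is (SD²/20)(1 + ρ), while the test assumes SD²/20. The reported standard error is therefore 1/√(1 + ρ) of the true one, and type I error is approximately 2[1 − Φ(1.96/√(1 + ρ))]. At ρ = 0.5, 1.96/1.225 = 1.60, which gives 0.110. Simulation (30,000 to 400,000 trials per figure) agrees, running slightly higher for the t-tests at high ρ:

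| ρ | SE ratio | Approximation | Between-product t | Within-arm t | Rank-sum | Signed-rank |
|---|---|---|---|---|---|---|
| 0.2 | 0.91 | 0.074 | 0.075 | 0.072 | 0.067 | 0.070 |
| 0.5 | 0.82 | 0.110 | 0.113 | 0.111 | 0.110 | 0.105 |
| 0.8 | 0.75 | 0.144 | 0.154 | 0.153 | 0.146 | 0.144 |
| 0.9 | 0.73 | 0.155 | 0.168 | 0.169 | 0.161 | 0.158 |

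**2. One value per subject.** With the two folds averaged, simulated type I error of the t-tests is 0.048 to 0.051, within and between arms, at every correlation tried. The exact rank-sum test gives 0.042 to 0.048. Averaging or summing makes no difference to any of these tests: the sum is twice the mean, so t statistics, ranks and p-values are identical.

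**3. Effect of the Day 0 biopsy.** Let it shift the measured change on that fold by b.
- Within arm, the two-fold mean moves by b/2.
- Between products, an equal b gives b/2 − b/2 = 0.
- Rough scale: a 3-mm core has volume π × 1.5² × depth. At assumed depths of 2 to 6 mm this is 14.1 to 42.4 mm³, so half is 0.007 to 0.021 mL. Against the per-fold session maxima in Section 7.6, that is 0.9% to 2.8% of 0.75 mL (CaHA) and 0.16% to 0.47% of 4.5 mL (PLLA). Healing or swelling could shrink or reverse it.

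**4. Cost of using only the unbiopsied fold within arm.** Its variance is SD²/10, against SD²(1 + ρ)/20 for the two-fold mean, a ratio of 2/(1 + ρ). The 95% half-width is t(9)/√10 = 0.72 SD, against 0.72 × √((1 + ρ)/2) SD. Mean squared errors are equal when b²/4 = SD²(1 − ρ)/20, that is b = 2√((1 − ρ)/20) SD.

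| ρ | Extra variance | Half-width, two-fold mean | Half-width, one fold | Break-even b |
|---|---|---|---|---|
| 0.2 | 67% | 0.55 SD | 0.72 SD | 0.40 SD |
| 0.5 | 33% | 0.62 SD | 0.72 SD | 0.32 SD |
| 0.8 | 11% | 0.68 SD | 0.72 SD | 0.20 SD |
| 0.9 | 5% | 0.70 SD | 0.72 SD | 0.14 SD |

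Reporting the biopsied-minus-unbiopsied difference by arm would settle little. Its SD is √(2(1 − ρ)), so with 10 subjects the 95% half-width is 0.90 / 0.72 / 0.45 / 0.32 SD across the four correlations.

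**The case for a change.** The strongest case for a change is that Section 10.2 speaks of each fold and Section 11 never moves from fold to subject. Naming completing subjects defines the population, not the observation. Folds, a mean or one chosen fold would all comply, and such choices are best fixed before data are seen. Both volume tests are affected, and a remedy would need wording only, since both folds are imaged and the biopsy side is on the randomisation list.

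The within-arm change is also a planned result, and a biopsy effect can mislead there. With no product effect and averaged folds, the chance of a false improvement (nominally 2.5%) is 5.5% to 6.7% if b = +0.25 SD and 0.7% to 1.0% if b = −0.25 SD.

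The silence on the unit stands, and so does the arithmetic. The inference that the plan must change does not. The inflation needs an analysis that no section proposes and that disregards subject-level randomisation. The ±0.25 SD scenarios cannot be tied to anything in the documents, which give no SD and no biopsy effect. If the biopsy lowers volume, the test for improvement is conservative.

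The unbiopsied fold is not a clean standard either. The Day 0 biopsy comes before injection, the investigator then chooses the amount, and both folds must receive the same amount, so the biopsied fold could influence what the other receives. The within-arm change also has no untreated control, so removing b/2 would still not isolate a product effect.

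**Conclusion.** The omission is real but needs no change. The Synopsis counts subjects per product, Section 7.5 assigns product by subject, and Section 11 compares two treatments among completing subjects. A competent analyst reads this as 10 values per arm, each combining a subject's two folds, and that holds the nominal error rate. The 7% to 17% figures describe a misreading under an assumed 5% level and assumed correlations of 0.2 to 0.9.

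The biopsy question is a fair trade-off. The two-fold mean carries b/2 within arm and nothing between products if the effect is equal; a product-specific effect is possible but not shown. Using the unbiopsied fold removes b/2 at a cost of 5% to 67% more variance with 10 subjects. It has lower mean squared error only if b exceeds 0.14 to 0.40 SD. If it were used only within arm, the two within-arm changes would no longer subtract to the reported product difference. For a secondary endpoint in 20 completers, with b unknown in size and direction, keeping both folds is reasonable.
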